9 DATA ANALYSIS / STATISTICAL METHODS

This section briefly describes the planned statistical methods for this study. A SAP will describe the methods in detail. If there is a difference between the language of this protocol and the language of the SAP, the SAP will take precedence over the protocol.

9.1 Randomization

No randomization is applied in this study.

9.2 General Considerations

Tables and listings will present results by age cohort and starting dose and will include demography, subject disposition, baseline disease characteristics and other medical history, and concomitant medications. Efficacy variables and analyses are discussed in Section 9.4. Safety variables and analyses are discussed in Section 9.5.

All analyses of potassium levels will use central laboratory values. The potassium values obtained locally and used to manage subjects' dose levels at study sites, may also be used in estimating missing central laboratory values.

The efficacy and safety populations will include all subjects who have taken at least one dose of patiomer. For subjects who transition to maintenance hemodialysis or peritoneal dialysis during the study, their data after the start of dialysis will be excluded from summary statistics and will be included in listings only.

9.3 Sample Size Determination

The sample size was selected in a manner that will maximize information for selected starting doses while minimizing exposure of children to ineffective starting doses. The initial number of subjects per age/dose cohort will be 3. When the DSMC agrees that a safe and effective starting dose (i.e., the recommended dose) has been identified for a particular age group, nine additional subjects in the age group will receive the selected starting dose. This will yield a total of 12 subjects per age group. The total sample size for all three age groups could be as low as 36, if the first dose is chosen as safe and effective, and up to 54 if all three dose levels are studied for each age group.

With a sample size of 12 subjects in each age cohort at the identified efficacious and safe starting dose, and assuming a 100% probability of achieving potassium level within the normal range (3.8 – 5.0 mEq/L), the lower bound of the 95% exact confidence interval for achieving this success rate is 73%.

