--

	stopping patiromer treatment (Follow-up Visit 2). All subjects who withdraw early from treatment will enter the Follow-up Period.
DSMC Review / Starting Dose Level Assessment:	
The DSMC will determine a recommended starting dose for each age group. After three subjects at a given starting dose level provide data from the 14-Day PD / Dose Finding Phase, the DSMC will evaluate safety and PD data, including achievement of serum potassium within the target range (serum K⁺ 3.8 – 5.0 mEq/L) and the PD response pattern as well as the number of subjects requiring dose titration. Based on this review, the DSMC will provide a recommendation to evaluate another starting dose in the age group or to evaluate the current starting dose in additional subjects in the age group. Details regarding DSMC review criteria will be described in a charter and are summarized in the DSMC section of the protocol (Section 8.6).
 
The initial number of subjects for each starting dose level will be three, and up to three starting doses per age group can be evaluated. Subject screening will pause periodically throughout the study to allow for preparation of data and DSMC review and provision of recommendations. Any subjects who are in the Screening Period when the pause is announced may be enrolled provided they meet all eligibility criteria. When the Study Management Committee (SMC; see Section 8.5) and DSMC agree upon the recommended patiromer starting dose for a particular age group based upon safety and PD data review, nine additional subjects (or fewer if more than three subjects were initially enrolled) will be added in that age group to receive the recommended patiromer starting dose. Subjects will not be enrolled into higher starting dose levels once the recommended patiromer starting dose is determined for a particular age group. This will yield a total of 12 subjects per age group at the recommended starting dose and a maximum of 18 subjects per age group.
 
Based on findings from the 12 – < 18 years of age cohort, the DSMC will provide a recommendation to initiate dosing in a younger age group, and provide further guidance regarding the starting doses and titration increments for the younger age groups.
 
In addition, the DSMC will review safety and PD data on an ongoing basis during the Long-Term Treatment Phase for all age groups.

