Once the initial group of subjects at a given starting dose level complete their 14-Day PD / Dose Finding Phase, PD and safety data will be provided to the DSMC. The DSMC will evaluate safety and PD data, as well as the number of subjects requiring dose titration. Based on its review, the DSMC will determine if the starting dose for subjects under review was appropriate, in which case, nine additional subjects (or fewer if more than three subjects were initially enrolled) in the same age group will be enrolled at the same starting dose. If the DSMC determines that the starting dose did not result in an acceptable PD response, and the safety is acceptable, the DSMC will provide a recommendation to evaluate the next starting dose in the age group (see Section 8.6 for detailed information on the DSMC).

Subject screening will pause periodically throughout the study to allow for preparation of data and DSMC review and provision of recommendations. Any subjects who are in the Screening Period when the pause is announced may be enrolled provided they meet all eligibility criteria.

Patiromer dose titration is allowed per a protocol-specified algorithm (See Section 5.2.1). The titrated increment or decrement is planned to be the lowest starting dose for each age group.

All patients treated in the PD / Dose Finding Phase will be included in the Long-Term Treatment Phase.

3.2.3 Long-Term Treatment Phase:

After completion of the 14-Day PD / Dose Finding Phase, subjects then enter a Long-Term Treatment Phase that consists of eight visits over a period of 5.5 months. Study visits consist of Week 3, Week 5, Week 7, Week 10, Week 14, Week 18, Week 22 and Week 26 (see Appendix B). Dose adjustments in the Long-Term Treatment Phase may be made at each study visit starting with the Week 2 (Day 14) Visit according to the titration algorithm (see Section 5.2.1).

At each study visit in the Long-Term Treatment Phase, potassium levels will be measured locally and by central laboratory. ECG evaluations will be performed as soon as possible whenever the local K⁺ level is > 6.0 mEq/L; at the Week 26 (or ET) Visit, an ECG will be performed regardless of potassium level. Additional laboratory assays and assessments will be performed according to the Schedule of Events (see Appendix B). A full list of central laboratory assays is provided in Appendix C.

Study visits at Week 3, Week 10 and Week 22 are optional and may be omitted under the following circumstances:

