- Other: the subject's participation in the study was terminated for a reason other than those listed above. The Investigator must specify the detailed reason.

In addition, a variety of reasons may lead either Relypsa or a regulatory agency to terminate the study early, in which case all subjects would be withdrawn from the study.

It is important to collect information explaining why subjects withdrew from the study. This information, together with AEs occurring at those times, may be very informative of the cause-specific reasons for why some subjects remain in the study or on the assigned treatment while others do not. Therefore, although the subject's legally authorized representatives are not obliged to give their reason for withdrawing consent, the Investigator will make a reasonable effort to obtain the reason while fully respecting the subjects' rights. Reasons for withdrawal of consent, when provided by the subject's legally authorized representatives, will be recorded in the electronic case report form (eCRF). The procedures described for Early Termination (ET, see Section 6.4) will be performed, if possible. Every effort will be made to contact the legally authorized representatives of a subject who fails to attend a study visit, or does not respond by telephone, in order to ensure that the subject is in satisfactory health. The Investigator will immediately inform the Medical Monitor of removal or early withdrawal of a subject from the study.

If a subject withdrew within the 14-Day PD / Dose Finding Phase, the DSMC may be consulted regarding possibility of replacing the withdrawn subject.

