8.5 Study Management Committee

The SMC includes Sponsor representatives and the lead study investigator. The SMC will review data from the study on an ongoing basis. Within pre-specified guidelines, the SMC will have the authority to make modifications to the study dose and titration plan between meetings of the independent DSMC. For instance, the SMC could extend the number of subjects being treated in an age/dose cohort, even if no specific safety issues were encountered, to allow collection of additional data. The prespecified guidelines will be detailed in the DSMC Charter and SMC Plan.

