8.6.1 Dose Escalation

Evaluation of Starting Dose Levels:

During the 14-day PD / Dose Finding Phase the Investigator will be allowed to up-titrate the patiromer dose according to a protocol-specified algorithm. A description of the patiromer dose titration algorithm is provided in Section 5.2.1.

After three subjects complete their 14-Day PD / Dose Finding Phase, PD, dosing and safety data will be provided to the DSMC. The DSMC will evaluate these data, as well as the number of subjects requiring dose titration. Based on its review, the DSMC will determine if the starting dose for subjects under review was acceptable for a recommended starting dose, in which case nine additional subjects (or fewer if more than three subjects were initially enrolled) in the same age group will be enrolled at the same starting dose. If the DSMC determines that the starting dose and/or titration pattern did not result in an acceptable PD response, but the safety was acceptable, the DSMC will provide a recommendation to evaluate the next higher starting dose in the age group.

Subject screening will pause periodically throughout the study to allow for preparation of data and DSMC review and provision of recommendations. Any subjects who are in the Screening Period when the pause is announced may be enrolled provided they meet all eligibility criteria. Details regarding DSMC review criteria are described in the DSMC charter.

The DSMC will evaluate the following subject-level parameters in assessing a patiromer starting dose level:

- Achieving a target serum potassium range of 3.8 – 5.0 mEq/L
- Clinically relevant decrease in serum potassium
- Number of dose up-titrations above the starting dose
- Patient safety information

The DSMC will consider the baseline and change in serum potassium level in determining if an observed decrease in serum potassium is clinically relevant for subjects that do not achieve the target potassium range. In addition, the DSMC will consider the proportion of subjects that had up-titrations of patiromer to ensure a recommended starting dose is close to the effective dose (e.g., up-titrations required in all three subjects may suggest the starting dose was too low).

Section 5.2 describes the planned starting doses in all age groups. The DSMC will recommend the starting doses for the 6 – <12 year old age group upon evaluation of PD and safety data for the

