entire 12 – <18 year old age group through Day 14. Similarly, such an evaluation also will occur when the entire 6 – <12 year old group completes Day 14 in order to recommend starting doses for the 2 – <6 year old group.

8.6.2 *Stopping Criteria*

Safety Criteria:

The safety profile of patiomer in children > 2 years of age is expected to be similar to the safety profile of patiomer observed in adults (see Section 1.2).

In addition to the AEs mentioned in

Table 5 (see Section 8.2.3) that will be evaluated by the Investigator based on the descriptions in

Table 5 (see Section 8.2.3), the DSMC will review all other AEs (including SAEs) using standard severity descriptors (mild, moderate and severe) included in the protocol. The DSMC will also review all central laboratory data, including occurrences of serum magnesium and potassium below the lower limit of normal as provided in the laboratory reports (see Section 8.6).

Deaths that are assessed as due to hypokalemia will be assessed as related to the investigational drug. Deaths that are assessed as due to hyperkalemia will be assessed as due to failure of the investigational drug.

Study or Dose Level Stopping Criteria:

- If two subjects experience the same severe GI AEs that in the opinion of the Investigator(s) and SMC **are related to patiomer**, the DSMC will be consulted to review the available safety data and either provide approval to continue dosing for all subjects or make recommendations regarding modification of starting dose and/or titration algorithms within an age group and sequentially in younger age groups by dose category
- If two subjects experience medically similar unexpected SAEs that in the opinion of the Investigator and SMC **are related to patiomer** the DSMC will be consulted to review the available safety data and either provide approval to continue dosing for all subjects or make recommendations regarding modification of starting dose and/or titration algorithms within an age group and sequentially in younger age groups by dose category
- If one subject experiences an unexpected SAE that is confirmed **to be related to patiomer**, no additional subjects in the same age cohort will be started on or up-titrated to the dose level at which the SUSAR occurred

For individual subjects experiencing any unexpected drug-related SAE or AE leading to withdrawal, the SMC will review the event and the DSMC will be notified at an ad hoc basis.

8.6.3 *Frequency of DSMC Meetings*

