14-Day PD / Dose Finding Phase

The DSMC will meet after all three subjects in each age and dose cohort complete their 14-day PD / Dose Finding Phase to review their safety, dosing and pharmacodynamic data as described in

Section 8.6. An additional DSMC meeting will occur after the dose expansion group (n = 9) provide sufficient information from their 14-day PD / Dose Finding Phase. If a subject withdraws from the study within the 14-Day PD / Dose Finding Phase, the SMC will determine if sufficient information is provided for DSMC review. If insufficient information is provided, the DSMC meeting may be delayed.

Long-Term Treatment Phase

The DSMC will meet at regular intervals to conduct ongoing review of PD, dosing and safety data throughout the Long-Term Treatment Phase to monitor safety and evaluate the effectiveness of patiomer dose titration algorithms. The DSMC may make recommendations to modify the patiomer dose titration algorithms based upon their review. Additional details are provided in the DSMC Charter.

Ongoing DSMC Review

During the study, ad-hoc DSMC meetings may be requested by either the DSMC or SMC to review relevant information that may have an impact on patiomer dosing or the safety of the participants in the study.

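### If all three starting doses are tried in an age group, can 12 at the recommended dose and a maximum of 18 both be kept?

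*Protocol*

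**What the plan says.** Protocol 9.3 and SAP 2.3 start each age/dose cohort with three subjects, add nine at the dose chosen, and arrive at 12 per age group. They give a study total between 36 and "up to 54 if all three dose levels are studied for each age group". The synopsis (DSMC Review / Starting Dose Level Assessment) states the same per age group: "12 subjects per age group at the recommended starting dose and a maximum of 18 subjects per age group".

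Three provisions can take a dose group above three:

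- Protocol 3.2.2 and 8.6.1, on pauses for data review: "Any subjects who are in the Screening Period when the pause is announced may be enrolled provided they meet all eligibility criteria".
- Protocol 8.5: "the SMC could extend the number of subjects being treated in an age/dose cohort, even if no specific safety issues were encountered". This power is exercised within guidelines that the section assigns to the DSMC Charter and the SMC Plan.
- Protocol 4.3, for a withdrawal during the first 14 days: "the DSMC may be consulted regarding possibility of replacing the withdrawn subject".

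One offset is written down, in the synopsis and in Protocol 1.4, 3.2.2 and 8.6.1: "nine additional subjects (or fewer if more than three subjects were initially enrolled) in the same age group will be enrolled". It shortens the expansion at the selected dose. Protocol 9.3 and SAP 2.3 give nine without that qualifier, and Protocol 8.6.3 describes the review after the expansion this way: "An additional DSMC meeting will occur after the dose expansion group (n = 9) provide sufficient information".

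**The concern.** If an age group works through all three doses, there is no spare place between 12 and 18. A single extra child at a rejected dose then forces either 19 in the age group or 11 at the recommended dose. The offset does not help, because it acts only at the dose that is selected. Nor do the protocol and SAP say whether a child who was dosed and then replaced counts toward 18 and 54.

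The stakes would be the stated ceiling on the number of children exposed, or else the precision at the recommended dose, with the choice made in an open-label trial after the rejected-dose data are known. The start of the next younger cohort also depends on when an age group is complete: Protocol 8.6.1 waits until the 6 to under 12 "year old group completes Day 14 in order to recommend starting doses for the" youngest group, and has the same step between the oldest and middle groups.

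**Working it through.** **Inputs.** Three initial subjects per dose, nine added at the chosen dose, up to three doses per age group and three age groups (Protocol 3.2.2 and 9.3). Target 12 and maximum 18 per age group (synopsis). Lower bound 73% for 12 successes out of 12 (Protocol 9.3, SAP 2.3).

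**The plan's own figures.**

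- Minimum: 3 × (3 + 9) = 36.
- Maximum: 3 × (3 + 3 + 3 + 9) = 54, which is 18 per age group.
- Two-sided 95% exact lower bound when all n succeed: 0.025^(1/n). For n = 12 this is 0.7354, or 73.5%, given in the plan as 73%.

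All are reproduced.

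**When 12 and 18 collide.** Let R be the number of subjects at rejected doses in one age group. Both figures hold when 12 + R ≤ 18, that is, R ≤ 6.

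- First dose chosen: R = 0. Extra starters are absorbed by the offset and the total is 12.
- Second dose chosen: R is one group, planned at 3. It could double to 6 before the cap is reached.
- Third dose chosen: R is two groups, planned at 3 + 3 = 6. There is no slack.

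So only the three-dose case can bind under modest over-enrolment. The documents give no figure for over-enrolment; R = 7 and R = 8 below are illustrative.

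| R | Age-group total if 12 is kept | n at recommended dose if 18 is kept | Lower bound, all n succeed |
|---|---|---|---|
| 6 | 18 | 12 | 73.5% |
| 7 | 19 | 11 | 71.5% |
| 8 | 20 | 10 | 69.2% |

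**Study total.** If all three age groups used all three doses with R = 8 and kept 12, the total would be 3 × 20 = 60. But an age group that settles on its second dose uses 12 + 3 = 15 as planned. One group at 19, one at 18 and one at 15 gives 52, still under 54.

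**Primary endpoint.** The 95% half-width for a mean is t(0.975, n−1)/√n × SD, with multiplier 0.6354 at n = 12 and 0.7154 at n = 10. For an assumed SD of 0.3 to 0.8 mEq/L, this is 0.19 to 0.51 at n = 12 and 0.21 to 0.57 at n = 10.

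**The unqualified nine.** With five starters at the selected dose, adding a flat nine gives 5 + 9 = 14. Protocol 9.3 and SAP 2.3 cannot mean that: both state a premise of three starters and a result of 12. With the offset, 12 − 5 = 7 are added and the result is again 12.

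**The case for a change.** The best case for a change is that the trigger is built into the plan. Groups larger than three are foreseen, or the offset would not exist, and neither the pause rule nor Protocol 8.5 itself gives a numerical limit. Everyone who takes one dose is in both analysis populations (Protocol 9.2; SAP 4.1 and 4.2), so a replaced subject stays in those populations while the counting rule is unstated. The SAP takes precedence over the protocol, and it is the SAP that lacks the qualifier on nine. A sentence or two would settle all of this.

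Part of this stands. The protocol and SAP are silent on which number has priority and on how replaced subjects count. The wording on nine is uneven.

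The rest is weaker. The pause rule reaches only children already inside a screening period of up to seven days (Protocol 3.1). The extension and the replacement are discretionary; the first is bound by the Charter and SMC Plan, and the second is a matter on which the DSMC may be asked. Those two documents were not available, so an absence of any rule is unproven. Making the choice after seeing rejected-dose data adds no clear bias, since dose selection here is data-dependent by design and reviewed by an independent DSMC. The review in Protocol 8.6.3 turns on sufficient information having been provided, so an expansion of fewer than nine does not block it.

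**Conclusion.** This is a minor ambiguity in an unlikely contingency, and the stated figures do not contradict one another. Under the planned scheme 12, 18, 36, 54 and 73% all agree. The two per-age-group numbers part only if all three doses are used and the rejected groups total more than six.

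The limits on 18 and 54 are worded as ceilings and can be read that way without further text. Should the 12 shrink as a result, the loss is about two percentage points of a best-case bound for each of the first two subjects. No hypothesis test or power target depends on it. Tables are produced by age cohort and starting dose with the number of subjects shown (SAP 7.1), so a group of 11 would be visible as such.

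Writing a priority rule would settle a fair trade-off between exposure and precision that the sponsor and DSMC can resolve if it arises. Aligning the references to nine would be tidy, but it changes no estimate. The conclusion rests on over-enrolment of one or two subjects, an assumption the documents neither confirm nor rule out, and on the analysis remaining descriptive as planned.

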9.4 Efficacy Analysis

9.4.1 Primary Efficacy Variable

Changes from baseline to Day 14 in serum potassium levels will be summarized by starting dose and age group using descriptive statistics. Baseline potassium will be the last central laboratory serum potassium value prior to first dose of patiromer. Descriptive statistics include mean, standard deviation, and 95% confidence intervals.

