2 TRIAL OBJECTIVES

Primary: To assess change from baseline in serum K^+ levels to Day 14 following administration of different doses of patiromer administered once daily in children 2 – < 18 years of age with CKD and hyperkalemia.

Secondary: To assess the safety and tolerability of patiromer in children 2 – < 18 years of age with CKD and hyperkalemia.

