During the 14 Day PD / Dose Finding Phase, patiromer dose up-titration by the permitted titration increment for each age group is allowed beginning at Day 7 for K^+ value > 5.0 mEq/L. Dose titration may not be required if the potassium decrease from the previous visit was ≥ 0.5 mEq/L. Patiromer dose down-titration by the permitted titration decrement for each age group or more is allowed for any K^+ value < 3.8 mEq/L to a minimum patiromer dose of 0 g/day. If patiromer dose requires titration, then initiation of the titrated patiromer dose should occur at the next planned administration.

Day 3 Safety Assessment: As a safety measure to ensure that subject exposure to hyperkalemia is not prolonged, the patiromer dose may be up-titrated at Day 3 only if the K^+ level is ≥ 5.5 mEq/L and is greater than the most recent locally obtained screening potassium value. Note: At the discretion of the Investigator, the Day 3 Visit is optional for subjects whose last screening K^+ is < 5.5 mEq/L; for subjects whose last screening K^+ is ≥ 5.5 mEq/L, the Day 3 Visit is mandatory (see Section 6.2.2).

During the Long-Term Treatment Phase, patiromer dose up-titration by the permitted titration increment for each age group is allowed for any K^+ value > 5.0 mEq/L. Dose titration may not be required if the potassium decrease from the previous visit was ≥ 0.5 mEq/L. Patiromer dose down-titration by the permitted titration decrement for each age group, or more, is allowed for any K^+ value < 3.8 mEq/L to a minimum patiromer dose of 0 g/day. If patiromer dose requires titration, then initiation of the titrated patiromer dose should occur at the next planned administration.

A description of the patiromer dose titration algorithm for each age group is described in Figure 2 below.

Figure 2: Planned Patiromer Dose Titration Algorithm.

^a At Day 3, as a safety measure to ensure that subject exposure to hyperkalemia is not prolonged, patiromer dose may be up-titrated only if the K⁺ level is ≥ 5.5 mEq/L and is greater than the most recent locally obtained screening potassium value. Note: At the discretion of the Investigator, the Day 3 Visit is optional for subjects whose last screening K⁺ is < 5.5 mEq/L; for subjects whose last screening K⁺ is ≥ 5.5 mEq/L, the Day 3 Visit is mandatory (see Section 6.2.2).

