6.2.3 Day 7 Visit

Patiromer dose may be adjusted on Day 7 based on the potassium level measured locally according to the titration algorithm. A description of the patiromer dose titration algorithm is provided in Section 5.2.1.

The activities for Day 7 (± 3 days) are detailed below and in Appendix A:

- Subject's visit registration in IWRS
- Vital Signs (resting heart rate and sitting BP)
- 12-Lead ECG (Only if local K⁺ is > 6.0 mEq)
- Blood or serum potassium levels (measured locally) and serum potassium measured by central laboratory
- Serum chemistry (measured by central laboratory)
- Patiromer dose titration (if needed), dispensation, reconciliation, accountability, compliance, and subject retraining (as applicable)
- Review of Subject Dosing Diary by Investigator and/or designee
- Assessment of AEs
- Assessment of concomitant medications
- Next visit scheduling

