2 STUDY OBJECTIVES AND STUDY DESIGN

2.1 Study Objectives

2.1.1 *Primary Efficacy Objectives*

To assess change from baseline in serum potassium levels to Day 14 following administration of different doses of patiromer administered once daily in children 2 – < 18 years of age with chronic kidney disease (CKD) and hyperkalemia.

2.1.2 *Safety Objectives*

To assess the safety and tolerability of patiromer in children 2 – < 18 years of age with CKD and hyperkalemia.

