7.6 Exposure to Study Drug

The actual prescribed dose of patiromer by cohort, starting dose, and study day will be summarized.

A listing for drug exposure will be provided.

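### Does grouping the Day 14 potassium change by starting dose defeat the dose-finding aim, given that doses are titrated before Day 14?

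*Protocol*

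**What the plan says.** The primary objective is the change in serum potassium to Day 14 "following administration of different doses of patiromer administered once daily in children" aged 2 to under 18 (Protocol 2; SAP 2.1.1 has the same objective). Protocol 9.4.1 and SAP 5.1.1 report it by starting dose and age group: "Changes from baseline to Day 14 in serum potassium levels will be summarized by starting dose and age group using descriptive statistics". The summary is descriptive, with a mean, SD and 95% confidence interval.

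The dose can move before Day 14 (Protocol 5.2.1):

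- Routine increase, for potassium above 5.0 mEq/L: "patiromer dose up-titration by the permitted titration increment for each age group is allowed beginning at Day 7".
- Day 3 exception: "the patiromer dose may be up-titrated at Day 3 only if the" potassium is at least 5.5 mEq/L and above the latest local screening value.
- Decrease: "Patiromer dose down-titration by the permitted titration decrement for each age group or more is allowed for any" potassium below 3.8 mEq/L, down to 0 g/day.

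The step equals the lowest starting dose of the age group, and a new dose begins at the next planned administration.

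The Day 7 visit includes "Blood or serum potassium levels (measured locally) and serum potassium measured by central laboratory" (Protocol 6.2.3), plus central serum chemistry. On dose, SAP 7.6 states: "The actual prescribed dose of patiromer by cohort, starting dose, and study day will be summarized".

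**The concern.** The objective speaks of different doses, and the 14-day phase exists to choose a dose. Titration depends on the outcome: a child who responds poorly is moved up, and the Day 14 value still counts for the starting dose. This pulls the starting-dose groups together and could make a weak starting dose look adequate. The central Day 7 sample is drawn before any routine increase takes effect, yet no named efficacy analysis uses it to isolate the response to the starting dose. The SAP summarizes prescribed dose separately and does not relate it to potassium. If the recommended dose rested on the Day 14 table alone, it could be set too low.

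**Working it through.** **1. The plan's own figures.** Protocol 9.3 gives 3 children per initial age/dose group and 12 at the recommended dose. Totals: 3 × (3 + 9) = 36 and 3 × (3 + 3 + 12) = 54, as stated. The exact two-sided lower bound for 12 of 12 is 0.025^(1/12) = 0.735, against a stated 73%. These figures reproduce. They fix the group sizes used below and do not otherwise bear on the question.

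**2. Overlap in dose taken.** Starting doses and steps are from Protocol 5.2 and 5.2.1. The table allows up to two increases at scheduled visits (Day 3 and Day 7) before the Day 14 sample.

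| Age (years) | Lowest start (g/day) | Middle start (g/day) | Highest start (g/day) |
|---|---|---|---|
| 12 to <18 | 4.2, 8.4, 12.6 | 8.4, 12.6, 16.8 | 16.8, 21.0, 25.2 |
| 6 to <12 | 2, 4, 6 | 4, 6, 8 | 8, 10, 12 |
| 2 to <6 | 1, 2, 3 | 2, 3, 4 | 4, 5, 6 |

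Adjacent groups overlap in every cohort. Lowest and highest groups do not overlap through these increases. Two steps require the narrow Day 3 exception as well as a Day 7 increase. Mandatory Safety Visits also permit titration (Protocol 6.5.1) and are not counted here.

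Time on a changed dose before the endpoint varies with the visit windows. After a Day 7 change it is 11 − 10 = 1 day to 17 − 4 = 13 days. After a Day 3 change it can reach 17 − 2 = 15 days.

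**3. Loss of contrast.** The documents give no paediatric dose-response, so every figure in this step rests on assumptions.

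*Hand illustration.* Assume effects of −0.4, −0.8 and −1.0 mEq/L at 4.2, 8.4 and 12.6 g/day, with 60% of low starters and 20% of middle starters raised once.

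- Low: 0.4 × (−0.4) + 0.6 × (−0.8) = −0.64
- Middle: 0.8 × (−0.8) + 0.2 × (−1.0) = −0.84

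A difference of 0.40 appears as 0.20, a 50% loss. This is a single scenario, and it gives titrated children the full average effect of the higher dose although they were raised because they responded poorly.

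*Simulation of the titration rules, age 12 to <18.* Assumed: maximum effect 0.8 to 1.6 mEq/L, half-maximal dose 4.2 to 16.8 g/day, underlying mean potassium 5.4 to 5.7 mEq/L, between-child and measurement SDs 0.3 each, response time constant 2.5 days.

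| Quantity | Range |
|---|---|
| 4.2 g/day starters on a higher dose by Day 14 | 27% to 91% |
| 4.2 g/day starters with a dose change at Day 3 | 4% to 32% |
| 4.2 vs 8.4 g/day contrast at Day 7 (mEq/L) | 0.093 to 0.256 |
| Same contrast at Day 14 (mEq/L) | 0.073 to 0.210 |
| Day 14 contrast as share of Day 7 | 66% to 82% |
| 4.2 vs 16.8 g/day, Day 14 as share of Day 7 | 74% to 96% |

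The 4.2 versus 8.4 g/day contrast thus loses 18% to 34%. In absolute terms the loss runs from 0.093 − 0.073 = 0.020 to 0.244 − 0.167 = 0.077 mEq/L. Day 7 is itself not wholly free of titration, because of the Day 3 changes.

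**4. Precision.** Half-width of a 95% interval for a mean = t × SD / √n. The SD of 0.454 mEq/L is that of the maximal reduction in the adult onset-of-action study (Protocol 1.2). It is assumed for children, with a range of 0.3 to 0.6.

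- n = 3: 4.303 × 0.454 / √3 = 1.13 (range 0.75 to 1.49)
- n = 12: 2.201 × 0.454 / √12 = 0.29 (range 0.19 to 0.38)
- Difference, 3 against 12 children, common SD: 2.160 × 0.454 × √(1/3 + 1/12) = 0.63 (range 0.42 to 0.84)

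The half-width of the difference exceeds the simulated Day 7 contrast (at most 0.256) even at SD 0.3. In the 36-child scenario each age group has a single starting dose, and there is no contrast to lose.

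**5. What is already planned.**

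- SAP 7.9.2 graphs central potassium and its mean change at every scheduled visit.
- SAP 7.10.3 summarizes chemistry results and change from baseline at every scheduled visit. Potassium is in that panel (Protocol Appendix C).
- SAP 7.1 lays tables out by age cohort and starting dose with n, mean, SD and SE, so a Day 7 interval is mean ± t × SE.
- SAP 7.6 gives prescribed dose by starting dose and study day, which shows how far each group moved.

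**6. How the dose is chosen.** Protocol 8.6.1 has the DSMC weigh attainment of the target range, a clinically relevant fall, the number of up-titrations and safety. It says that increases in all three children may mean the starting dose was too low. This is a direct guard against a weak starting dose passing on its Day 14 values.

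**The case for a change.** The best case for a change is that the study report is built on the SAP, and the SAP places no pre-titration efficacy result beside the primary one. The by-visit chemistry table is a safety output without a stated confidence interval. The layout by starting dose is written for tables, not graphs, and nothing flags children whose dose changed at Day 3. At the recommended dose, about 12 children per age group would give a Day 7 mean a half-width near 0.29 mEq/L, which is informative even if only one starting dose is tested. The data exist, and the cost is one table.

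The description is accurate: Day 7 is not labelled as an efficacy analysis, and the Day 3 flag is absent. But the table would add a label and an interval to numbers already planned. It would change neither the primary result nor the dose decision.

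Splitting Day 14 change by titration status or by dose at Day 14 would do harm. Poor responders receive the higher doses, so higher doses would look less effective, and cells could hold one or two children. Taking the last value before any dose change would also mix Day 3 and Day 7 exposure times, and for a child never titrated it would be the Day 14 value itself.

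**Conclusion.** No change is needed. Day 14 change by starting dose describes a start-and-titrate strategy. That is a fair summary for a study whose product is a recommended starting dose within a titrated regimen. Adjacent groups can overlap in dose taken, and this shrinks the contrast between them: by 18% to 34% for 4.2 versus 8.4 g/day, or 0.02 to 0.08 mEq/L, relative to Day 7. Those figures rest on the assumed dose-response curves in step 3, as the documents give none for children. The contrast is not a planned inference: levels are opened in sequence without randomization, the analysis is descriptive, and a rejected level usually has three children, with a half-width near 1.13 mEq/L if the adult SD applies. The DSMC reviews up-titrations explicitly, and the planned tables already carry the Day 7 change and the prescribed dose for each starting-dose group. An analyst writing the report can set these beside the Day 14 result without amending the SAP.
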